### Contraception Guidance

#### Male participants

Male participants with female partners of childbearing potential are eligible to participate if they agree to the following:

1. Are abstinent from penile-vaginal intercourse as their usual and preferred lifestyle (abstinent on a long-term and persistent basis) and agree to remain abstinent for duration of study and for 4 days from last dose
2. Female partner is using a highly effective contraceptive method
3. Agree to use a male condom plus an additional method with a failure rate of <1% per year as described in the table below when having penile-vaginal intercourse with a woman of childbearing potential.
4. Men with a pregnant or breastfeeding partner must agree to remain abstinent from penile-vaginal intercourse or use a male condom during each episode of penile penetration and for 4 days from last dose.
5. Refrain from donating sperm for duration of study and for 4 days from last dose.

Highly Effective Contraceptive Methods That Are User Dependent  Failure rate of <1% per year when used consistently and correctlya.

Combined (estrogen and progestogen-containing) hormonal contraception associated with inhibition of ovulationb
 
 
• Oral
 
• Intravaginal
 
• Transdermal
 

Progestogen-only hormonal contraception associated with inhibition of ovulationb
 
 
• Oral
 
• Injectable
 

Highly Effective Methods That Are User Independent

 
• Implantable progestogen-only hormonal contraception associated with inhibition of ovulationb
 
• Intrauterine device (IUD)
 
• Intrauterine hormone-releasing system (IUS)
 
• Bilateral tubal occlusion
 

Vasectomized partner  (A vasectomized partner is a highly effective contraception method provided that the partner is the sole male sexual partner of the woman of childbearing potential and the absence of sperm has been confirmed. If not, an additional highly effective method of contraception should be used.)


Sexual abstinence  (Sexual abstinence is considered a highly effective method only if defined as refraining from heterosexual intercourse during the entire period of risk associated with the study treatment. The reliability of sexual abstinence needs to be evaluated in relation to the duration of the study and the preferred and usual lifestyle of the participant.)

NOTES:
 
a) Typical use failure rates may differ from those when used consistently and correctly. Use should be consistent with local regulations regarding the use of contraceptive methods for participants participating in clinical studies.
 
b) Hormonal contraception may be susceptible to interaction with the study treatment, which may reduce the efficacy of the contraceptive method. In this case, 2 highly effective methods of contraception should be utilized during the treatment period and for at least 4 days from last dose.

## Female participants

Female participants of reproductive potential are eligible to participate if they agree to use a highly effective method of contraception consistently and correctly as described in the table above.

## Pregnancy Testing

Women of childbearing potential should only be included after a confirmed menstrual period and a negative highly sensitive serum pregnancy test.

Additional pregnancy testing should be performed at regular intervals as per the SoA during the treatment period and at 28 days after the last dose of study treatment.

Pregnancy testing will be performed whenever a menstrual cycle is missed or when pregnancy is otherwise suspected.

Pregnancy testing, with a sensitivity of 5 mIU/mL will be performed and assayed at the study site.

## **Collection of Pregnancy Information**

### **Male participants with partners of reproductive potential who become pregnant**

Investigator will attempt to collect pregnancy information on any female partner of a male study participant who becomes pregnant while participating in this study. This applies only to participants who receive study treatment.

If a pregnancy is reported for a subject's partner, study treatment will be immediately discontinued.

After obtaining the necessary signed ICF from the pregnant female partner directly, the Investigator will record pregnancy information on the appropriate form and submit it to the DCC within 24 hours of learning of the partner's pregnancy.

Partner will also be followed to determine the outcome of the pregnancy. Information on the status of the mother and child will be forwarded to the DCC.

Generally, follow-up will be no longer than 6 to 8 weeks following the estimated delivery date. Any termination of the pregnancy will be reported regardless of fetal status (presence or absence of anomalies) or indication for procedure.

### **Female participants who become pregnant**

Investigator will collect pregnancy information on any female participant who becomes pregnant while participating in this study.

Information will be recorded on the appropriate form and submitted to the DCC within 24 hours of learning of a participant's pregnancy.

Participant will be followed to determine the outcome of the pregnancy. The Investigator will collect follow-up information on participant and neonate, which will be forwarded to the DCC. Generally, follow-up will not be required for longer than 6 to 8 weeks beyond the estimated delivery date.

Any termination of pregnancy will be reported, regardless of fetal status (presence or absence of anomalies) or indication for procedure.

While pregnancy itself is not considered to be an AE or SAE, any pregnancy complication or elective termination of a pregnancy will be reported as an AE or SAE.

A spontaneous abortion is always considered to be an SAE and will be reported as such.

Any SAE occurring as a result of a post-study pregnancy that is considered reasonably related to the study treatment by the Investigator will be reported to the DCC as described in [Appendix 4](#). While the Investigator is not obligated to actively seek this information in former study participants, he/she may learn of an SAE through spontaneous reporting.

Any female participant who becomes pregnant while participating will be withdrawn from the study.

**Appendix 7: Summary of Versions and Changes**

Protocol	Version	Date	Summary of Change
Original	1.0	September 5, 2018	Not Applicable
Revision 1	1.1	October 26, 2018	Eligibility and safety modifications per FDA request (see also Table of Protocol changes October 26, 2018)
Revision 2	1.2	July 31, 2019	Eligibility and safety modifications (see also Table of Protocol changes July 31, 2019)
Revision 3	1.3	February 18, 2020	Eligibility modifications to include participants on augmentation therapy and safety updates (also see Table of Protocol changes February 18, 2020)
Revision 4	1.4	February 10, 2021	Eligibility modifications to include participants with other rare genotypes/phenotypes at increased risk for emphysema. (also see Table of Protocol changes February 16, 2021)

# 1 Abbreviations and Definitions

Abbreviation	Description
AAT	Alpha-1antitrypsin
AATD	Alpha-1 antitrypsin deficiency
Aα-Val360	Fragment from neutrophil elastase cleavage of elastin at Aα-Val360 site
AcPGP	Acetylated Proline-Glycine-Proline
AE	Adverse event
AESI	Adverse event of special interest
ALT	Alanine aminotransferase
ANCOVA	Analysis of covariance
AST	Aspartate aminotransferase
AUC	Area under the curve
BAL	Bronchoalveolar lavage
bid	Twice (2 times) a day
C1M	MMP-derived collagen type I breakdown fragment
C6M	MMP-derived collagen type VI breakdown fragment
CAT	COPD assessment test
Catio	Cathensin G
CF	Cystic fibrosis
CFR	United States Code of Federal Regulations
CMP	Complete metabolic profile
CMV	Cytomegalovirus
CONSORT	Consolidated Standards of Reporting Trials
COPD	Chronic obstructive pulmonary disease
CRE	Case report form
CRO	Clinical Research Organization
CT	Computerized or computed tomography
	Cutochromo P450 2C0
	Data Coordinating Contor
ЫС З	Desiliosine
	Decinite Data Safaty Manitoring Roard
	Enstein Borr virus
EDV	Electrocardiogram
	Electronic case report form
	Elastin degradation mediated by Cathepsin G
	Elastin lika polyportido 2
EL-PS	Elastin like polypeptide 5
	End of treatment
	Elastin peptide 3
	Full Analysis Set
	Forced expiratory volume in 1 second
	Forced expiratory volume in T second divided by the forced vital capacity
FU	Follow-up
FVU	
y CCD	Gram
GCP	
	HOUR
ncg	
HIV	Human Immunodeticiency virus

Abbreviation	Description					
hsCRP	High-sensitivity C-reactive protein					
HRT	Hormone replacement therapy					
HSV	Herpes simplex virus					
Hy's Law	a rule of thumb that a patient is at high risk of a fatal drug-induced liver injury (DILI) if given a medication that causes hepatocellular injury (not cholestatic injury) with jaundice					
IC50	the concentration of an inhibitor where the response (or binding) is reduced by half					
ICF	Informed consent form					
ICH	International Conference on Harmonization					
IEC	Independent Ethics Committee					
IL-1β	Interleukin 1 beta					
IL-6	interleukin-6					
IL-8	interleukin-8					
IND	Investigational new drug					
INR	International normalized ratio					
IRB	Institutional Review Board					
IWRS	Interactive web response system					
Ki	Inhibitory constant					
kPa	kiloPascal, a unit of force					
LSM	Liver stiffness measurement					
I TB4	Leukotriene b4					
MedDRA	Medical Dictionary for Regulatory Activities					
mGv	milliGray, a unit of radiation					
ma/dl	Milligrams per decilitre					
mg/dE	Milli International Units					
MMP	Matrix metalloproteinase					
MMRC	Modified medical research council					
MOP	Methods of procedures					
MPO	Myeloperovidase					
MS	Millisecond					
mS\/	milliSever					
NCATS	National Center for Advancing Translational Science					
NCAIS	National Clinical Trial					
	National Olinical Inal					
	National Institutes of Health					
	National institutes of fleat lovel					
	Non storoidal anti inflammatory drug					
NSAID Do	Ron-steroldal alti-illianinatory drug					
га	Pascal					
	Alpha 1.77 construct					
	Alpha 1 SZ genotype					
	Alpha 1 Null construct					
	Alpha-1 Null genotype					
PGP	P-glycoprotein					
PKS	Pharmacokinetics Set					
PR DDO						
PPS	Per Protocol Set					
PR	time from the onset of the P wave to the start of the QRS complex on ECG					
PR3	Proteinase 3					

Abbreviation	Description
PROs	Patient reported outcomes
PRO-C6	Released C-terminal pro-peptide of type VI collagen
QRS	Represents ventricular depolarization on ECG
QT	The duration of ventricular depolarization and repolarization on ECG
QTc	Corrected QT interval
QTcF	QTc by Fridericia's correction method
QTcV	QTc by Van de Water's correction formula
RANTES	Regulated on activation, normal T cell expressed and secreted
RBC	Red blood cell
SAE	Serious adverse event
SAF	Safety Set
SAP	Statistical Analysis Plan
SAS	Statistical analysis software
SGRQ-C	St. George's Respiratory Questionnaire compact version
SoA	Schedule of Activities
SOB	Shortness of breath
SOP	Standard operating procedure
SOBQ	Shortness of breath questionnaire
Sp02	Pulse oximetry
SUSAR	Suspected Unexpected Serious Adverse Reaction
ТВ	Total bilirubin
ug	Microgram
ULN	Upper limit of normal
uM	Micromolar
UPs	Unanticipated problems
VZV	Varicella zoster virus
WBC	White blood cell
Wk.	Week

# 2 Introduction

# 2.1 Preface

This is a Phase 2, multicenter, double-blind, randomized (1:1), placebo-controlled, 12-week, proof-of-concept study to evaluate the safety and tolerability as well as the mechanistic effect of oral administration of Alvelestat (MPH966) in subjects with confirmed AATD defined as Pi\*ZZ, Pi\*SZ, Pi\*null, or another rare phenotype/genotype known to be associated with either low (serum AAT level <11  $\mu$ M or <57.2 mg/dL) or functionally impaired AAT including "F" or "I" mutations.

# 2.2 Purpose

The purpose of this Statistical Analysis Plan (SAP) is to provide detailed descriptions of the statistical methods, data derivations and data displays for the ATALANTa study; to ensure that the data listings, summary tables and figures which will be produced, and the statistical methodologies that will be used, are complete and appropriate to allow valid conclusions regarding the study objectives.

# 3 Study Objectives

### 3.1 Primary Objectives:

- To evaluate the effect of Alvelestat (MPH966) administered twice daily (bid) for 12 weeks on blood markers of neutrophil elastase activity
- To evaluate the safety and tolerability of Alvelestat (MPH966) administered twice daily (bid) for 12 weeks

# 3.2 Secondary Objectives

- To evaluate the effect of Alvelestat (MPH966) on other blood pharmacodynamic markers of neutrophil activation and elastase activity
- To evaluate the effect of Alvelestat (MPH966) on blood biomarkers of lung tissue degradation
- To evaluate the effect of Alvelestat (MPH966) on biomarkers of inflammation in blood

# 3.3 Exploratory Objectives

- To evaluate the effect of Alvelestat (MPH966) on respiratory symptoms, breathlessness, and health status
- To evaluate PK efficacy relationships in AATD
- To evaluate the effect of Alvelestat (MPH966) on neutrophil activation, elastase, and inflammatory activity in lung. This was a secondary outcome but now exploratory depending on data available for analyses due to sputum and BAL being optional.

# 3.4 General Study Design and Plan

This will be a multicenter, double-blind, randomized, placebo-controlled trial. One dose of Alvelestat (MPH966), 120 mg bid, will be tested against placebo. These doses are based on PK and PD modelling of Alvelestat (MPH966) inhibition of human neutrophil elastase.

The participants will be those patients with the AATD at risk for emphysema (Pi\*ZZ, Pi\*SZ, Pi\*null, or another rare phenotype/genotype known to be associated with either low [serum AAT level <11  $\mu$ M or <57.2 mg/dL] or functionally impaired AAT including "F" or "I" mutations)

Following a screening period of up to 4 weeks, patients will be dosed with study treatment or placebo for 12 weeks, with a subsequent 4-week follow-up period for safety and determination of the offset of the mechanistic effect of MPH966 on the primary endpoint (desmosine/isodesmosine).

The study is divided into 3 phases: a screening phase, treatment phase, and washout phase as detailed below:

#### Figure 1: Study Schematic

- Red arrow = Randomization Blue arrow = Blood (biomarker) collection Green arrow = Sputum collection Orange arrow = BAL collection
- A screening period from Week -4 to Day -1. Baseline safety assessments and measurement of DES in blood, sputum, and BAL (in those who consent to bronchoscopy) will occur prior to randomization and treatment allocation.
- A treatment period consisting of Alvelestat (MPH966) 120mg bid or placebo for 12 weeks. Safety assessments including tests of liver function, ECG, hematology, and chemistries will be assessed at the week 1 and week 2 visits and then bi-weekly for the remainder of the 12-week treatment period. Blood will be collected at the Week 4, 8, and 12 visit for biomarker analysis. Sputum will be collected at the week 12 visit. Follow-up BAL will be collected at week 11.
- **A washout period** from Week 12 to Week 16. Blood will be collected for biomarker analysis at week 16.

# 3.5 Inclusion-Exclusion Criteria and General Study Population

### 3.5.1 Inclusion Criteria

Participants are eligible to be included in the study only if ALL of the following criteria apply:

Type of Participant and Disease Characteristics

- 1. Capable of giving signed informed consent as described in Appendix 3, which includes compliance with the requirements and restrictions listed in the informed consent form and in this protocol
- 2. Age  $\geq$ 18 and  $\leq$ 80 years
- 3. Patients with a confirmed diagnosis of AATD: Pi\*ZZ, Pi\*SZ, Pi\*null, or another rare phenotype/genotype known to be associated with either low (serum AAT level <11 μM or <57.2 mg/dL) or functionally impaired AAT including "F" or "I" mutations.
- 4. FEV1 ≥25% predicted
- 5. Patients will be eligible if they are either a) are not currently receiving augmentation treatment and have not received augmentation in the 12 weeks prior to screening or b) have received weekly infusions of augmentation at 60 mg/kg for at least 12 weeks prior to screening and intend to continue augmentation through the study period.
- 6. Male or female sex
  - a. Male participants must agree to use a highly effective contraception as detailed in Appendix 5 during the treatment period and for at least 4 days after the last dose of study treatment and refrain from donating sperm during this period
  - b. Female participants are eligible to participate if not pregnant; not breastfeeding; and at least one of the following conditions is met:

i. Not a woman of childbearing potential as defined in Appendix 5 OR

ii. A woman of childbearing potential who agrees to follow the contraceptive guidance in Appendix 5. During the treatment phase and for at least 4 days after the last dose of study medication.

# 3.5.2 Exclusion Criteria

Participants are excluded from the study if ANY of the following criteria apply:

#### **Excluded Medical Conditions**

- 1. Subjects with Pi\*MZ, Pi\*FM, Pi\*MS, Pi\*SS, or other AATD phenotypes/genotypes not known to be independently associated with emphysema.
- 2. Any clinically diagnosed lung disease other than COPD such as diffuse interstitial lung diseases, cystic fibrosis, or clinically significant bronchiectasis as determined by the Investigator
- 3. Acute exacerbation of underlying lung disease requiring oral steroids and/or antibiotics within 4 weeks of baseline
- 4. Acute or chronic hepatitis, including hepatitis B, hepatitis C (positive serologies, including hepatitis B and C antibody)
- 5. HIV infection or other immunodeficiency or with an absolute neutrophil count ≤1.0 × 109/L
- Abnormal liver biochemistry (alanine aminotransferase, aspartate aminotransferase, gamma-glutamyl transferase) >1.5 × upper limit of normal or total bilirubin > upper limit of normal (unless Gilbert's disease with normal conjugated bilirubin)
- 7. Any of the following laboratory abnormalities are present at baseline:
  - a. Platelet count <150×109/L
  - b. Serum albumin  $\leq 3.5 \text{ g/dL}$
  - c. INR ≥1.2
  - d. CPK ≥ ULN.

- 8. History or current evidence of cirrhosis (on biopsy or imaging), esophageal varices, ascites or hepatic encephalopathy.
- 9. Evidence of other forms of chronic liver disease based on diagnostic testing as per the guidelines (i.e. autoimmune liver disease, primary biliary cirrhosis, primary sclerosing cholangitis. Wilson's disease. Hemochromatosis or iron overload).
- 10. Patients with nonalcoholic fatty liver disease (NAFLD) as diagnosed by any imaging modality (or use of drugs associated with NAFLD for more than 2 weeks in the year prior to screening).
- 11. Subjects with a history of significant alcohol consumption for a period of more than 3 consecutive months within 1 year prior to screening, defined as average of >20g/ day in female subjects and >30g/ day in male subjects.
- 12. Fibrosis-4 (FIB-4) score >3.25
- 13. Any of the following cardiovascular conditions within 6 months prior to the screening visit:
  - a. Myocardial infarction or unstable angina
  - Coronary artery bypass surgery, balloon angioplasty, percutaneous coronary b. intervention, or carotid revascularization procedure
  - Uncontrolled hypertension C.
  - Stroke or transient ischemic attack d.
- 14. Congestive heart failure (New York Heart Association III/IV) with left ventricular election fraction < 40%
- 15. Any clinically significant 12-lead electrocardiogram abnormalities at screening or baseline, including corrected QT interval by Fridericia's correction method >450 ms or history of significant cardiac dysrhythmia, including long QT syndrome
- 16. History of cancer within the last 5 years, except for well-treated basal cell carcinoma and squamous cell carcinoma of the skin
- 17. Other documented comorbidities or laboratory abnormalities that in the opinion of the Investigator could affect the outcome of the study assessments, participant safety, or ability of the participant to comply with the requirements of the protocol

#### Excluded Prior/Concomitant Therapy

- 18. Daily use of prednisone (>10mg daily), or other systemic glucocorticoids at comparable or higher equivalent dose, or use of other immunosuppressant therapies are prohibited
- 19. Immunomodulating monoclonal antibodies within 6 months prior to screening are prohibited
- 20. Daily use of non-steroidal anti-inflammatory drugs (NSAIDs) is prohibited. Daily use of acetaminophen up to 2 g per day and aspirin up to 325 mg per day is permitted.
- 21. Initiation of drugs known for hepatotoxic potential within the 28 days prior to screening including but not limited to: statins, NSAIDS, amoxicillin/clavulanate, PDE inhibitors (theophylline, roflumilast), and anti-epileptics. Subjects on established treatment for more than 28 days prior to screening will not be excluded. Requirement for medications mainly metabolized by CYP2C9 and with narrow therapeutic index (eq, warfarin, phenytoin) is prohibited

#### Excluded Prior/Concurrent Clinical Study Experience

22. Participation in any clinical investigation using medical devices or non-biologic treatments within 4 weeks or 5 half-lives of the drug (whichever is longer) prior to the initial dosing (or longer if required by local regulations) is prohibited

23. Participation in any clinical investigation using biologic treatment within 6 months of screening is prohibited

24. Previous participation in a gene therapy study for AATD at any time is prohibited

#### Other Exclusions

25. History of hypersensitivity to Alvelestat (MPH966) or any of its excipients or the class of neutrophil elastase inhibitors

26. Known hypersensitivity to medications used in the study procedures (e.g. midazolam, fentanyl, and lidocaine for bronchoscopy)

# 3.5.3 Sample Size

Over the course of the study, target enrolment is 66 with the goal of 60 completers. Participants will be randomized in a 1:1 ratio to receive one of the following: 120mg Alvelestat (MPH966) BID or placebo. Randomization will be stratified by AAT genotype/phenotype.

The study will be powered for within-individual change in plasma desmosine/isodesmosine (DES) as the primary endpoint at Week 12 compared to baseline. A sample size of 30 participants in the MPH966 treatment group will give us >90% power to detect a 15% mean decrease of plasma DES from baseline to 12 weeks follow-up in patients treated with MPH966 (within subject change) using a two-sided paired t-test at  $\alpha$ =0.05. The calculation is based on an assumed correlation value of 0.5, baseline mean DES value of 0.466 and standard deviation of 0.09. This 15% mean decrease has been observed in trials of standard dose augmentation versus placebo (Ma S, 2013). A recent study of double dose versus single dose augmentation revealed a within subject decrease in plasma DES from 0.42 +/-0.03 ng/ml to 0.38 +/- 0.03 ng/ml (Campos MA, 2019). We will have >99% power to detect a comparable difference in DES in those who have Alvelestat added to augmentation if we assume their observed SD=0.03 and 85% power if we double their assumed SD, i.e., SD=0.06. Power will not be enough (~50%) to detect this difference if we use our original SD value of 0.9.

For comparing the mean change in DES between the two groups (placebo vs. MPH966), and assuming that there is no placebo effect over 12 weeks, a two-sided two sample t-test at  $\alpha$ =0.05 with a sample size of 60 (30 per group) reveals that we will have 82% power to detect a 15% difference in mean change in plasma DES.

By including a 10% attrition rate over 12 weeks, the required sample size is inflated to 66 (33 per group) to achieve the estimated powers. If we observe attrition rate less than we expected, we will have more statistical power to detect the expected differences. As one interim analysis will be conducted only for safety concerns (see Data Safety and Monitoring Plan), no adjustments to the Type I error are considered for estimating statistical powers.

All participants will be centrally randomized 1:1 to the 120 mg and placebo arms using an interactive web response system (IWRS). A unique number will be assigned to each participant and will be linked to randomization numbers using a randomization list produced by the DCC. These randomization numbers will be linked to the 2 treatment regimens, and the randomization scheme will be stratified according to genotype (Pi\*ZZ, Pi\*SZ, Pi\*(Null) (Null))

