# 4 Endpoints

### 4.1 Primary Efficacy Endpoints

Within-individual % change from baseline in plasma desmosine/isodesmosine at end of treatment with MPH966

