# 8.1 Primary Efficacy Endpoint Analyses:

The primary outcome is the relative change from baseline at week 12 in plasma desmosine/isodesmosine levels within treatment group. Within individual relative (percent) change from baseline in plasma desmosine/isodesmosine levels will be analyzed using Mixed Model Repeated Measures (MMRM). Relative change (percent) from baseline will be considered the response variable, with time as main independent fixed effect variable and baseline levels, augmentation, age, and smoking history (yes/no) as a fixed effect covariates, using an unstructured covariance matrix to model the within-subject errors. Available data from all time points will be included. The least squared estimates of the mean at each Week and EndPoint will be generated. [Note: Originally, it was planned to use sputum strata and FEV1 as covariates in the model. However, due to the restrictions of the pandemic, there was limited opportunity to collect the required sputum, and therefore will not be included in the analyses.] The analysis will be conducted using the SAS 'proc mixed', with the below specific code:

proc mixed data=Data; by TRTP; class SUBJID TRTP AVISIT AUGMENTATION SMOKING; model PCTCHG = BASE AVISIT AUGMENTATION AGE SMOKING; ddfm=KENWARDROGER; repeated AVISIT/ subject=SUBJID type=UN; lsmeans AVISIT / pdiff; run;

where PCTCHG is the relative (percent) change from baseline, BASE are baselines values, TRT is treatment arm, AVISIT is Weeks, AGE is age at enrollment, SMOKING is yes/no at enrollment and AUGMENTATION (yes/no) at enrollment. If imbalances are found between treatment groups in baseline characteristics deemed to be clinically important in influencing the relative change in the outcome, sensitivity analyses will be performed by including these variables as covariates in the above model. P-value<0.05 for the mean difference at Week 12 will be deemed significant. Estimate including 95% confidence interval of the least squares mean difference will also be provided.

If any issues related to convergence occur and cannot be resolved within the 'proc mixed', then alternative procedures will be considered (such as 'proc glimmix'). Other covariance structures will also be considered if convergence is an issue with unstructured covariance. Transformation of data or alternative distribution for the model will be considered should there be evidence of nonnormality of the data.

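### The primary DES analysis tests change within an arm only, so it cannot attribute a fall to alvelestat; the SAP dropped the protocol's treatment contrast from it without saying so

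*SAP*

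**What the plan says.** The SAP treats the primary efficacy question as a within-arm one throughout.

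- **Endpoint (SAP 4.1):** "Within-individual % change from baseline in plasma desmosine/isodesmosine at end of treatment with MPH966". Protocol Sections 1 and 4 word the endpoint the same way.
- **Power (SAP 3.5.3):** "The study will be powered for within-individual change in plasma desmosine/isodesmosine"; specifically, "A sample size of 30 participants in the MPH966 treatment group will give us >90% power to detect a 15% mean decrease of plasma DES", by a two-sided paired t-test in that arm. Protocol 10.1 has the same basis.
- **Analysis (SAP 8.1):** "The primary outcome is the relative change from baseline at week 12 in plasma desmosine/isodesmosine levels within treatment group". The code opens "proc mixed data=Data; by TRTP; class SUBJID TRTP AVISIT AUGMENTATION SMOKING" and its model statement is "model PCTCHG = BASE AVISIT AUGMENTATION AGE SMOKING". There is no treatment or treatment-by-visit term.
- **Success rule (SAP 8.1):** "P-value<0.05 for the mean difference at Week 12 will be deemed significant". The text does not say which difference is meant.

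The comparison with placebo appears in two other places. In SAP 4.3 and 8.2, DES versus placebo is secondary endpoint 1, with a two-arm model and its own p<0.05 rule. SAP 3.5.3 gives that comparison 82% power, "assuming that there is no placebo effect over 12 weeks".

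The primary row of Protocol 10.3.1 differs: an ANCOVA with treatment as a factor, giving least-squares mean differences between the groups. SAP Section 10 records that a mixed model replaces this ANCOVA and gives missing data and use of all visits as the reason. It does not record that the treatment contrast left the primary analysis.

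**The concern.** A change from baseline in one arm is the sum of the drug effect and anything else that moves DES over 12 weeks. Randomisation and blinding separate the two only when the arms are compared, and the primary analysis does not compare them. A non-drug fall is credited to alvelestat; a non-drug rise is counted against it.

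Two features of the plan sharpen this. The 15% target is described in SAP 3.5.3 as seen in trials of standard-dose augmentation versus placebo, so a controlled effect is used to power an uncontrolled test. And neither document says what will be concluded if the within-arm test succeeds while the placebo contrast does not. A reader could then be told that the primary endpoint was met on a result that does not separate drug from time.

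**Working it through.** **Inputs (SAP 3.5.3).** Baseline mean 0.466, SD 0.09, correlation 0.5, n = 30 per arm, two-sided 5%, target fall 15%.

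**Derived quantities.** SD of change = 0.09 × √(2 × (1 − 0.5)) = 0.09. Target fall = 0.15 × 0.466 = 0.0699.

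**1. The plan's own power figures.**
- Within-arm paired t-test: noncentrality 0.0699 / 0.09 × √30 = 4.25 on 29 df. Power is 98.4%, which agrees with the stated >90%.
- Between-arm two-sample t-test: noncentrality 0.0699 / (0.09 × √(2/30)) = 3.01 on 58 df. Power is 84.1% against the stated 82%. The gap is small and conservative; 28–29 per group, or an SD near 0.0925, would give about 82%.

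**2. Smallest fall that reaches significance within the arm.** Critical t on 29 df is 2.045. 2.045 × 0.09 / √30 = 0.0336, and 0.0336 / 0.466 = 7.2%. At the assumed SD, an observed mean fall of about half the target gives p<0.05 whatever produced it.

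**3. Drug inert, DES falls for other reasons.** Same test, with noncentrality = fall / 0.09 × √30. The fall sizes are assumptions; the documents give none.

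| Assumed non-drug fall | Absolute | Noncentrality | Within-arm test significant in the favourable direction |
|---|---|---|---|
| 0% | 0 | 0 | 2.5% |
| 2.5% | 0.0117 | 0.71 | 10.1% |
| 5% | 0.0233 | 1.42 | 27.8% |
| 7.5% | 0.0350 | 2.13 | 53.8% |
| 10% | 0.0466 | 2.84 | 78.3% |

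A change shared by both arms cancels in the between-arm test, which stays at 5% two-sided in every row.

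**4. The opposite direction.** If DES rose 5% for non-drug reasons and the drug truly lowered it by 15%, the net fall in the active arm would be 15 − 5 = 10%. Within-arm power is then 78.3% (last row above), against 84.1% between arms.

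**5. What the SAP 8.1 code can return.** With `by TRTP` and `lsmeans AVISIT / pdiff`, the output is visit means and visit-to-visit differences inside each arm. None of it is an alvelestat–placebo contrast, so the success rule's mean difference cannot be read as one from this code.

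**Limit.** These are paired and two-sample t-tests on the absolute scale. The planned analysis is a covariate-adjusted MMRM of percent change, so the figures approximate it.

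**The case against.** The case for leaving the plan alone has real content.

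- *The placebo arm is not ignored.* The primary model is run in both arms, and DES versus placebo is secondary endpoint 1 with its own model and test. A shared fall would be visible in both. This stands, and it rules out any reading that the trial has no controlled test of DES.
- *The primary test is valid for its stated null.* A reader might infer that its false-positive rate is inflated. It is not: against no change within the arm it holds 5%. The rates above describe wrong attribution, not loss of type I error control.
- *Progression does not hang on one p-value.* A reader might take Protocol 3.1 to mean that a within-arm success decides on phase 3. It refers to the results of the study, and Protocol 3.2 and 5.4 base progression on the efficacy data together with safety and tolerability. SAP 6.6 calls the study signal-seeking and sets no hierarchy.
- *The drift is conjecture.* Nothing in the documents links alcohol avoidance to DES, tobacco cessation is encouraged but optional (Protocol 6.3.2), background therapy must be stable (Protocol 6.1, 7.6), no DES threshold governs entry, and samples go to one central laboratory (Protocol 9). No particular drift can be claimed. But its absence cannot be claimed either, and settling that is what the placebo arm is for.
- *The endpoint was chosen openly.* It is within-individual in both documents. That makes it disclosed; it does not make it evidence of drug effect.

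What remains unanswered is the missing rule for discordant results, and the removal of the treatment factor for a reason that did not require it: an MMRM handles missing visits equally well with treatment in the model.

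**Conclusion.** The point holds as a problem of attribution and of an undeclared change from the protocol. It should be fixed before unblinding, but it does not invalidate the trial, because the controlled comparison is already planned and separately powered. The 7.2% threshold depends on the SAP's SD, correlation and n; the 10/28/54/78% rates depend also on fall sizes that are assumed here.

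**What to change.** Before unblinding, reconcile Protocol 10.3.1 with SAP 4.1, 8.1 and 10:

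1. Fit one MMRM to both arms with BASE, AUGMENTATION, AGE, SMOKING, TRTP, AVISIT and TRTP*AVISIT. Base the efficacy conclusion on the Week 12 alvelestat-minus-placebo least-squares mean difference with its 95% CI, and name that contrast in the success rule. The SAP 8.2 model cannot simply be reused for DES: it has FEV1 as a covariate, although Section 10 drops analyses using spirometry, and it has no AUGMENTATION term.
2. Report the within-arm change in each arm, with 95% CI, as supportive.
3. State that a within-arm fall without a between-arm difference will not be reported as evidence of drug effect.
4. Record the change in SAP Section 10.

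**Cost.** No new patients, samples or assays. The work is SAP wording, the Section 10 entry, and a protocol clarification, because the within-individual endpoint and its power basis also stand in Protocol 1, 4 and 10.1; under Appendix 3 a protocol amendment needs IRB approval. Power for the conclusion becomes the stated 82% (84.1% recomputed) instead of >90% (98.4% recomputed). The change comes late, since SAP Section 11 reports the interim safety analysis as already done, so the text should say that it was made while treatment allocation was still blinded.
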